### **Informed consent process**

- Consent forms will be obtained in person from adult participants. All participants, including patients with autism and healthy subjects are adults and capable of understanding the consent form. However, some of our patients with autism have legal guardianship or legal authority representative by one of the parents because of money expenses and other. For these cases, we will ask for a signature from the parent as well as from the adult subject.
- We will ensure that compensation is in line with effort and time required for the study. We will ensure comprehension of the informed consent information by allowing time for questions, verbally summarizing the material with the subject instead of just having them read it and asking subjects to answer a few questions to gauge understanding.

**Communication of results:** given that we are including MRI scans, we will be asking a medical doctor to look at them to double check any un-anticipated or incidental findings (such as tumors or apparent lesions). We will communicate incidental findings with the participant in person (after contacting him by email), only if the medical doctor decides that the MRI scan should be reviewed by an expert neurologist with a medical MRI to double check some doubts. We will be reporting only apparent incidents that could be life-threatening to the subject. We are not equipped to share with the participant's minor or more subtle problems given that we are conducting a research MRI scan and not a medical MRI. Participants will be provided a copy of the MRI anatomy scan. General results of the study can be communicated with participants after publication.

**Compensation:** Patients with autism will receive a total of \$200 for their participation in 5 research visits (\$40 per visit). Healthy subjects will receive a total of \$80 for their research visit.

### **Statistical analysis:**

Power analysis (using G power 3.1 software) shows that a sample size of 50 subjects with ASD receiving 4 different treatments is needed to reliably detect (95% power) effect sizes small or larger (Cohen's  $d=0.2$ ) on one measure. In this study, we expect to find small to medium size effects of oxytocin inhalation on behavioral measures (based on previous meta-analysis of Bakermans-Kranenburg and Van I Jzendoorn. 2013). Authors found a combined effect size of  $d=0.32$  (95% confidence interval: 0.18-0.47). As mentioned above, we are planning to break the blind with  $N=25$  ASD subjects for a mid-way analysis, which is sufficient to detect effect sizes between medium and small (Cohen's  $d=0.3$ ). We expect larger effect sizes on measures of brain

activity (BOLD activity and functional connectivity). Therefore, these measures will be mainly analyzed during the mid-way analysis for potential publications. Of note, we are also planning to publish the combined analysis with the total number of subjects on the measures that were published mid-way to avoid any publication bias.

For healthy subjects, we need at least 30 subjects receiving on treatment to reliably detect (95% power) the differences between social and non-social conditions or emotional faces versus neutral faces in the aims above with an effect size between small and medium (Cohen's  $d=0.35$ ).

When comparing healthy subjects to patients with autism (placebo administration only), the above numbers are sufficient to reliably detect small effect sizes between groups (Cohen's  $d=0.2$ ) for one measure.

The PI will submit an annual report to the IRB and address whether the study is safe and whether it is appropriate to continue. This report will include compliance, review of eligibility, treatment review, summary of responses, survival, adverse events and safety monitoring rules.

Given that we do not expect serious adverse events and we are investigating the effects of this hormone on brain activity and behavior, we do not expect an early stopping.

There will be analysis at various stages of the trial. We might need to analyze the behavioral and physiological data for data monitoring committee, in any or to write reports to NIH about the progress. There will be analysis of primary outcome measures of the different aims (cited above) during mid-way analysis (when we break the blind half way at  $N=25$  of ASD). The analysis will also be conducted at the final stage of the trial.

Brain imaging procedures using MRI, fMRI will be conducted at the Biomedical Imaging Technology Center (BITC) at Emory. Anatomical Image Acquisition: participants will be positioned supine in the MRI scanner (Siemens, Magnetom Prisma, Trio 3T) with instructions to lie motionless. Padded head restraint will minimize head movement during scanning sessions, each of which will begin with a 15 second scout scan to localize the position of the brain within the magnet. This will be followed by T1-weighted MPRAGE scan (TR= 2300 ms, TE = 4 ms, matrix = 256x256, FOV=256, slice thickness = 1.00 mm, gap = 0 mm).

**For aim 1, the primary outcome measure** consists of investigating the effects of different treatments (3 doses of oxytocin and one dose of placebo) on brain functional connectivity at rest in patients with ASD, using fMRI. During resting state functional image acquisition (8 minutes), participants will be asked to remain awake and not moving. Image acquisition will be obtained using a multi-band slice accelerated gradient echo-planar imaging (EPI) pulse sequence 179, 180 with the following parameters: TR = 1000 ms, TE = 24 ms, matrix = 74 x 74, FOV = 220 mm, slice thickness = 2.0 mm, 64 axial slices, to reduce magnetic susceptibility artifact in the OFC region.

The aim of this analysis is to determine whether there is target engagement for intranasal oxytocin by demonstrating differences between doses of IN-OT on BOLD rsFC or whether there is a simple oxytocin effect. We define target engagement OXT effect (TEE-OXT) as any differential effect between a dose of OXT from another dose of OXT on brain or behavior. We define oxytocin effect

(OXT-Effect) as any differential effect between oxytocin (any dose) and placebo administration in ASD.

Initial preprocessing steps for single-subject resting-state fMRI data will be conducted with FSL software or SPM with the help and training of [name]. fMRI data will undergo standard preprocessing steps: realignment, slice-timing correction, volume registration, spatial normalization to MNI152 template, spatial smoothing with 5 mm FWHM Gaussian filter and temporal band-pass filtering (0.01-0.1 HZ). Corrections for head motion, whole-brain signals, ventricular signals, white matter signals. We will define specific regions of interest that includes the social brain network that we discussed in the sections above (MPFC, OFC, PCC, precuneus, insula, ACC, ventral striatum, amygdala, temporal areas, SMA etc). We will compare the functional connectivity between and within the different social brain networks (including the default, the salience network and temporal network) between the different treatment conditions. This analysis will be performed based on the GLM using corresponding regressors. We will also compute the rsFC between the different regions of interest by calculating a Pearson's correlation coefficient between the time series of the preprocessed functional MRI signals. In order to study target engagement effect on within network correlations, the resulting of the cross-correlation maps will be Fisher transformed to z-scores and fed into a 2-factor (4 treatment condition X 3 networks (default, salience, temporal); covariate: visit order) ANOVA. In order to study target engagement effect on between network correlations, the resulting of the cross-correlation maps will be Fisher transformed to z-scores and fed into a repeated Anova (4 treatment condition X 3 networks (Salience+Default; Salience+Temporal; Default+Temporal); covariate: visit order) ANOVA. In order to determine simple oxytocin effect, T-contrast maps will determine the differences in rsFC between placebo and each of the different doses of oxytocin. Multiple comparison correction will be conducted. The specificity of the results will also be conformed in a whole brain analysis. Given that baseline rs-FC is not acquired, and in order to account for non-specific fluctuations, we will use a two-stage GLM procedure during which we account for within-subject variability (across the different visits). Time regressor will be added to the model as a covariate to control for external factors that could influence rs-FC other than the treatment.

*The secondary outcome measure* consists of correlating the effects of treatments on rsFC with the clinical improvements following treatments and post scan in ASD. The variables consist of BB-CGI clinical score (that will be rated blindly by a physician) and a socio-emotional behavioral score (rated by PI or staff blindly) during the BB-CGI. These two variables will be analyzed separately as they are dependent (based on the same test) but answer two different questions. We will conduct correlation analysis (Spearman or Pearson) between TEE-OXT or OXT-effect on rsFC and behavioral and clinical improvements. Behavioral variables will include: emotional responses, gestures, eye contact with experimenter and synchrony).

**For aim 2:** *The primary outcome measure of the second aim* consists of investigating the differences between the effects of the different treatments on BOLD activity of socio-emotional brain regions in response to social cues (Face perception task) in ASD. ROI analysis will include regions such as inferior occipital cortex, fusiform gyrus, superior temporal cortex, intra-parietal sulcus, superior parietal lobule, nucleus accumbens, amygdala and OFC). In this analysis, we have two variables that we will contrast (BOLD signal in response to emotional faces versus

neutral faces) and 4 treatment conditions within subject design (8IU, 24IU, 48IU and placebo) with covariates (order of visits to control for familiarity effects given that the treatment conditions are completely randomized). The presence of TEE-OXT will consist of finding differences between different treatment conditions of OXT and not only between OXT and placebo. We will also compare each of these OXT treatments with placebo condition separately to study OXT-effect.

*The secondary outcome measure* will consist of studying the effects of different treatments on a behavioral measure that is recorded during the MRI scan of the FPT: visual fixation duration on facial stimuli. Here, we have one variable (duration of visual fixation or eye gaze on emotional and neutral faces) and 4 treatment conditions. We will analyze the data with ANOVA repeated measures for determining TEE-OXT and t-tests for simple OXT-effects.

**For aim 3:** *The primary outcome measure* of the third outcome measure consist of studying the different effects of treatments on BOLD activity of key brain regions (OFC, ventral striatum, inferior occipital cortex, fusiform gyrus, amygdala, superior parietal lobe, insula and ACC) while playing a social interactive ball-game in ASD. During this ball-game, we will analyze the BOLD brain activity during social output videos that will display either neutral or positive face expressions. We expect more rewarding brain regions to be more activated during the process of positive social feedback with oxytocin treatment. In order to determine TEE-OXT, we will conduct repeated ANOVA analysis with variables (BOLD activity in response to positive and neutral) and treatments (8, 24, 48, placebo). We will also investigate the general effect of TEE-OXT on the BOLD activity of socio-emotional brain regions in response to both positive and neutral faces with the variable (BOLD activity in response to all faces) and treatments. We will also investigate the differences between oxytocin treatment and placebo. We expect at least the doses of 24IU and 48IU to be different from placebo. Covariates such as visit order will be entered in the GLM model as a regressor to control for habituation effects.

*The secondary outcome measure* consists of studying the effects of treatments on behavioral outcome measure (post scanner on social learning). In this behavioral task, we will analyze the accuracy and reaction time in recognizing faces as familiar. We will conduct ANOVA and t-tests to compare the performance in these 2 variables (accuracy and reaction time) between the 4 treatment conditions.

**For aim 4:** *The primary outcome measure* of the fourth outcome measure consists of investigating the differences between treatments on the modulation of brain activity of reward brain regions in response to punishment and helpful behavior. In the GLM model, we will conduct an ANOVA or t-tests with 4 treatment conditions and the BOLD signal in NAcc, OFC, VTA and ACC.

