- At first, we will study the effects of IN-OT doses on the resting state functional connectivity between key socio-emotional brain regions (using fMRI) that are shown to be deficient in ASD. Resting state functional connectivity is a task-independent metric of brain activity that is based on correlations between low-frequency fluctuations of the blood oxygen level-dependent signal between several brain regions. It reflects the strength of a functional connection that is in good agreement with the underlying neuroanatomy but goes beyond simple monosynaptic connections as it provides a system-level understanding of brain function. The power of this technique lies in its relative ease of acquisition and stability within and across scans sessions making it ideal for longitudinal experimental designs, including assessments of different treatments. Task-free acquisition precludes equating levels of performance – or motivation – between individual participants and across comparison groups. Large-scale brain networks are of particular relevance to this study. These networks include the - default mode network (DMN), which is centered on nodes in the mPFC, the midline posterior cingulate cortex (PCC), and the parahippocampal gyrus that has been implicated in mindwandering, planning the future and reflections on the past. The salience network (SN) centered on nodes in the dorsal anterior cingulate cortex and the frontoinsular cortex and sometimes including the ventral striatum that is implicated in the facilitation of attentional orientation to internal or external stimuli. The insular cortex is also involved in interoception and mapping internal bodily and subjective feelings states that are found deficient in Autism and related to a lack of alexithymia. The executive control network (ECN) is centered on nodes in the dorsolateral PFC and the lateral posterior parietal cortex that are associated with attending to and processing exogenous, attentionally-driven executive function. SN and ECN: are task-positive networks, which mean that these regions are identified at rest but are also activated during performance of most cognitive tasks. DMN usually deactivates during task performance. An overactivation or a reduced deactivation of the DMN and reduced ECN activation leads to decrements in task performance for healthy subjects and various neuropsychiatric diseases (Sonuga-Barke and Castellanos, 2007). We are particularly interested in networks that are relevant to oxytocin intake as based on the increased expression of oxytocin receptors in the brain, function of IN-OT on the brain and deficits in ASD.

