### **Randomization and blinding**

**Clinical trial for ASD subjects:** The trial will be a double-blind, placebo-controlled, several doses of oxytocin, within subject design study. Patients will undergo 4 clinical visits (in addition to a first pre-clinical visit) during which they receive 12 puffs (6 in each nostril) of 8IU total, 24IU and 48IU oxytocin (syntocinon) and placebo (assigned randomly). The placebo will contain the same ingredients as syntocinon, except the active molecule oxytocin. This is essential for making sure that the patient does not recognize the type of treatment he is receiving. Hence, both patients and the experimenter will be blind to the type of the treatment administered.

The pharmacy IDS of Emory will be in charge of the randomization sequence and one of the staff members of the team (who is not involved in testing procedures) will be de-blinded.

We will break the blind after testing 25 patients with ASD to check the results half-way for a mid-point analysis. The mid-point analysis will focus on measures where effect sizes are anticipated to be large enough that the risk of false positives is minimal. We are expecting larger effect size on some measures and therefore we break the blind for those measures to be analyzed and published. Additional data on these measures will continue to be collected and we will attempt to publish the combined analysis at the end to avoid publication bias.

However, the data collection will continue until a sample size equal to 50. Given that we are facing challenges with ASD recruitment and that the study requires the participation in 5 long visits, it is possible that the study will stop at N=30 or 40, in case the PI was not able to recruit more ASD. We also expect dropouts after recruitment. We believe that we will be able to test 30 patients with ASD.

It is possible that this project will be funded by other grant funds which will allow adding more participants (more 50 ASD). In this case, the PI will submit an amendment accordingly.

**Healthy subjects:** There will be only one clinical visit for healthy subjects and they will all receive placebo spray (12 puffs, 6 per nostril). The study will be conducted in a single-blind design. The PI is aware that the subject is receiving placebo. However, the participant will be told that he might

receive oxytocin or placebo. This is important in order to control for the placebo effect on behavior and brain activity.

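### The power figures for d = 0.2, 0.3 and 0.35 do not reproduce as dz, or as raw-SD d at ordinary correlations, and the inputs behind them are not stated

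*Combined protocol and SAP*

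**What the plan says.** The power paragraph is in the Statistical analysis section of the combined protocol and SAP. It credits G*Power 3.1 with three within-subject statements:

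- **ASD, four treatments:** "a sample size of 50 subjects with ASD receiving 4 different treatments is needed to reliably detect (95% power) effect sizes small or larger", with the effect given as Cohen's d = 0.2 on one measure.
- **Mid-way look, N = 25:** "which is sufficient to detect effect sizes between medium and small", given as d = 0.3 with no power level attached.
- **Healthy subjects, two conditions:** "we need at least 30 subjects receiving on treatment to reliably detect (95% power", given as d = 0.35.

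A fourth statement says the same numbers suffice for d = 0.2 between the healthy and ASD groups.

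For behaviour, the paragraph cites a meta-analytic d of 0.32 (95% interval 0.18 to 0.47). For the imaging outcomes it says only "We expect larger effect sizes on measures of brain" activity, with no number.

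The planned tests are repeated-measures ANOVA and pairwise comparisons. For the Aim 2 gaze outcome: "We will analyze the data with ANOVA repeated measures for determining TEE-OXT and t-tests for simple OXT-effects". For the Aim 2 BOLD outcome: "We will also compare each of these OXT treatments with placebo condition separately to study OXT-effect". Neither is tied to the power figures. No alpha, sidedness or between-condition correlation appears anywhere in the documents. The metric is named (Cohen's d), but not the SD that standardises it. On recruitment, the Randomization and blinding section says "We believe that we will be able to test 30 patients with ASD".

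**The concern.** A within-subject d of 0.2 is a small target for 50 people, and 95% is a high power. The two go together only if the repeated measurements are very highly correlated or the number is not a d at all. The paragraph does not let a reader tell which.

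The behavioural (secondary) outcomes are where this matters most. A reader who sees 95% power for d = 0.2 beside an expected d of 0.32 will take those outcomes as comfortably covered, and may then read a null result as evidence of no effect. The unquantified claim of sufficiency at N = 25 also helps to justify breaking the blind half-way for publication.

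**Working it through.** **Inputs.** N, number of conditions and d come from the power paragraph: (50, 4, 0.2), (30, 2, 0.35) and (25, 4, 0.3). Assumed, because not stated: alpha 0.05 two-sided, correlation rho of 0, 0.5 or 0.8, and sphericity.

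**1. Attempt to reproduce the plan's figures, reading d as dz (mean difference over the SD of differences).** Paired t, noncentrality dz·√N, df N − 1.

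- d = 0.2, N = 50: 0.2 × √50 = 1.414, power 28.4%. 95% power needs 327 subjects.
- d = 0.35, N = 30: 0.35 × √30 = 1.917, power 45.8%. 95% power needs 109 subjects.
- d = 0.3, N = 25: 0.3 × √25 = 1.5, power 30.2%.

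One-sided testing gives 40% at N = 50 and 59% at N = 30.

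**2. Reading d as raw-SD d.** Here dz = d / √(2(1 − rho)), which equals d when rho = 0.5.

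| Case | rho 0 | rho 0.5 | rho 0.8 | rho needed for 95% |
|---|---|---|---|---|
| d = 0.2, N = 50 | 17% | 28% | 59% | 0.93 |
| d = 0.35, N = 30 | 26% | 46% | 83% | 0.87 |
| d = 0.3, N = 25 | 17% | 30% | 62% | 0.92 |

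**3. Omnibus ANOVA instead of a pairwise test.** lambda = f²·N·m/(1 − rho), df (m − 1) and (N − 1)(m − 1). The most favourable pattern of four means with range d gives f = d/2. For d = 0.2, N = 50, rho = 0.5: lambda = 0.1² × 50 × 4 / 0.5 = 4.0, power 35%. For 95%, rho must be about 0.89.

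**4. Reading the printed numbers as Cohen's f, rho = 0.5.**

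- f = 0.2, N = 50, m = 4: lambda = 0.04 × 50 × 4 / 0.5 = 16.0, power 92.7%. Power is 95% at rho of about 0.55.
- f = 0.35, N = 30, m = 2: lambda = 0.1225 × 30 × 2 / 0.5 = 14.7, power 95.9%.
- f = 0.3, N = 25, m = 4: lambda = 0.09 × 25 × 4 / 0.5 = 18.0, power 94.8%.
- Between-group 0.2 as a group-by-condition interaction, total N = 80, m = 2: lambda = 0.04 × 80 × 2 / 0.5 = 12.8, df 1 and 78, power 94.2%.
- Between-group 0.2 as a plain two-group comparison of 50 with 30 (f = 0.2 is d = 0.4): noncentrality 0.4 × √(50 × 30 / 80) = 1.732, df 78, power 40%.

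For two conditions d = 2f, so f = 0.2 and 0.35 correspond to d = 0.4 and 0.7.

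**5. Effect detectable with a paired test, two-sided 0.05, rho = 0.5.**

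| N | 95% power | 80% power |
|---|---|---|
| 50 | d = 0.52 | d = 0.40 |
| 30 | d = 0.68 | d = 0.53 |
| 25 | d = 0.75 | d = 0.58 |

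**6. Power for the cited behavioural d = 0.32, taken as raw-SD d.**

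| N | rho 0 | rho 0.5 | rho 0.8 |
|---|---|---|---|
| 50 | 35% | 60% | 94% |
| 30 | 22% | 40% | 76% |

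**The case against.** The best defence is that the inputs are missing, not shown to be wrong. With raw-SD d and a high enough correlation, 95% power is attainable, and the Introduction credits resting-state connectivity with "stability within and across scans sessions making it ideal for longitudinal experimental designs". That stands as far as it goes: the claims are not impossible. But the remark gives no coefficient and covers neither task BOLD nor behaviour. The correlation needed at N = 30 is also a different one, between conditions within a single scan session. If d is dz, no correlation helps, because it is already absorbed in the metric.

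A second defence is that this is only a labelling slip. The f reading puts all three within-subject figures between 92.7% and 95.9%, and an interaction test brings the between-group figure to 94.2%. This is the likeliest explanation, but it remains an inference. The text refers to a difference between groups, and resting-state data have no second condition with which to form an interaction. Even if the defence is right, the d label is wrong by a factor of two for two conditions.

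A reader might go further and say that N = 50 misses 95% even as f. The documents do not support that: the 92.7% rests on an assumed correlation of 0.5, and about 0.55 is enough.

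It is also fair that the ASD claim covers one measure only, that the standardisation of the cited d = 0.32 is not given, and that its power reaches 94% at N = 50 if the correlation is 0.8.

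**Conclusion.** The concern holds in conditional form. Read as dz, or as raw-SD d at ordinary correlations, the 95% claims for d = 0.2 and d = 0.35 and the claim of sufficiency for d = 0.3 do not reproduce. Taking two-sided 0.05 and correlation 0.5, power is 28%, 46% and 30%. The stated power is reached only at correlations for which the documents give no value and no support. A Cohen's f printed as d would explain most of the pattern, but only the G*Power input can settle it.

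A reader might infer that the trial is underpowered for its primary imaging outcomes. The documents do not support that either. They give no numeric effect for those outcomes beyond expecting it to be larger, so adequacy there can be neither confirmed nor refuted.

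**What to change.** - Check the G*Power input. State the test, alpha, sidedness, between-condition correlation and standardiser, and the power meant at N = 25.
- If f was entered, relabel the figures as f and give the power at the correlation used: about 93% at N = 50 if it was 0.5, 95% if it was about 0.55.
- Otherwise withdraw the 95% claims for d = 0.2 and d = 0.35, and the claim of sufficiency for d = 0.3, unless a supporting correlation is justified.
- Restate the detectable pairwise d with its correlation (step 5 of the working).
- Report power for the behavioural d = 0.32 over a range of correlations at N = 50 and N = 30 (step 6), noting that the plan does not say how that d is standardised.

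The cost is a rewritten paragraph with less favourable figures, unless f or a high correlation is documented. Enrolment does not change: the Healthy subjects screening section reports that the patient group has been completed, and the healthy target of 30 stays as it is.

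### The ASD power statement covers a four-condition comparison that includes placebo; no power is given for the dose-versus-dose comparison that defines target engagement

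*Combined protocol and SAP*

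**What the plan says.** The Statistical analysis section of the combined protocol and SAP gives one sample-size statement for the main ASD cohort. It is introduced by "Power analysis (using G power 3.1 software) shows that" and continues that "a sample size of 50 subjects with ASD receiving 4 different treatments is needed to reliably detect (95% power") effects of Cohen's d=0.2 or larger on one measure. The four treatments are placebo and 8, 24 and 48 IU. For the mid-way analysis, N=25 is called sufficient for d=0.3, without restating a power level. Alpha, test, within-subject correlation and sphericity correction are not given.

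On expected effects, the section says "we expect to find small to medium size effects of oxytocin inhalation on behavioral measures" and cites a meta-analytic d=0.32 (95% CI 0.18 to 0.47). For imaging it says only "We expect larger effect sizes on measures of brain" activity, with no figure.

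For aim 1, the analysis is to establish target engagement "by demonstrating differences between doses of IN-OT on BOLD rsFC or whether there is a simple oxytocin effect". The target-engagement effect (TEE-OXT) is defined as "any differential effect between a dose of OXT from another dose of OXT on brain or behavior"; the oxytocin effect is defined as any dose against placebo. The aim 2 text adds that TEE-OXT needs differences among the oxytocin conditions, beyond a difference from placebo. Yet the test named for target engagement in aim 1 is an ANOVA with all four treatment conditions, and the aim 3 repeated ANOVA for TEE-OXT also lists placebo among its treatments.

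**The concern.** The power statement and the target-engagement definition concern different comparisons. A four-condition test draws on every difference among the conditions, including those between placebo and the doses. A dose-versus-dose comparison uses only what separates 8, 24 and 48 IU. If the response rises with dose, part of the signal behind the 95% comes from placebo and is lost once placebo is removed.

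Two things are at stake. A null dose comparison could be given more weight than the design supports, because the only power figure in sight is 95%. In the other direction, a significant four-condition ANOVA could be reported as target engagement when only placebo differs.

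**Working it through.** **Inputs.** From the plan: N=50, four within-subject conditions, 95% power, d=0.2; N=25 with d=0.3; a possible stop at 30 or 40 patients (Randomization and blinding). Assumed, because the plan is silent: two-sided alpha 0.05, repeated-measures ANOVA on one measure, sphericity, within-subject correlation rho=0.5 unless varied, and the dose-response shapes below.

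**1. The plan's own figure.** For a within-subject F test with m conditions, λ = N·m·f²/(1−rho), with m−1 and (N−1)(m−1) degrees of freedom.
- Literal d=0.2: the largest f for a range of 0.2 SD is 0.1. λ = 50×4×0.01/0.5 = 4 and power is 35%. Reaching 95% would take 216 patients, or rho of about 0.89.
- 0.2 entered as f: λ = 50×4×0.04/0.5 = 16 and power is 92.7%. Reaching 95% at N=50 needs rho of about 0.55.
- The other statements also fit f: N=25 with f=0.3 gives 94.8%; the healthy-control figure (N=30, two conditions, f=0.35) gives 95.9%.

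So the 95% does not reproduce from d=0.2 at rho=0.5. It nearly does if f was reported as d, which the documents do not say. Steps 2 to 4 take the 95% at face value.

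**2. Three-dose F test, N=50.** 95% power with 3 and 147 degrees of freedom needs λ = 17.6. Removing placebo leaves λ₃ = 17.6 × SS₃/SS₄, where SS₄ and SS₃ are the sums of squared deviations of the four means and of the three dose means. The test then has 2 and 98 degrees of freedom. Example, linear in IU (means 0, 8, 24, 48): SS₄ = 400+144+16+784 = 1344; SS₃ = 810.7; share 0.603; λ₃ = 10.6.

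| Shape (placebo, 8, 24, 48 IU) | SS₃/SS₄ | Power, three doses |
|---|---|---|
| Linear in IU | 0.603 | 83% |
| Equal steps (0, 1, 2, 3) | 0.400 | 65% |
| Half-maximum at 24 IU | 0.345 | 58% |
| Plateau from 24 IU (0, 0.5, 1, 1) | 0.242 | 43% |
| Step (0, 0, 1, 1) | 0.667 | 87% |
| Only 48 IU differs (0, 0, 0, 1) | 0.889 | 95% |

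If 95% is also meant at N=25 (λ = 18.1), the results are almost the same.

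**3. Dose pairs, same λ.** The noncentrality is √(17.6 × (μᵢ−μⱼ)²/(2·SS₄)). For linear, equal steps and half-maximum at 24 IU in turn, 48 versus 8 IU has 89%, 74% and 67%, and 48 versus 24 IU has 48%, 26% and 16%. On the same three shapes, 48 IU versus placebo has 97%.

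**4. What the four-condition test can show.** If all doses are equal and differ from placebo, SS₃ = 0. The four-condition F test still rejects 95% of the time, although there is no target engagement.

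**5. Literal d=0.2 between two doses.** dz = d/√(2(1−rho)), noncentrality dz·√N, paired t test. At rho=0.5, dz=0.2: N=50 gives 1.41 and 28%; N=30 gives 1.10 and 19%. At N=50, power is 22% for rho=0.3 and 87% for rho=0.9.

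**The case against.** The strongest reply is that the aim has two branches. Comparisons with placebo are planned throughout, so a power statement for a design that serves both branches is not misplaced. That stands: a reader might infer that dose against dose is the whole aim, and the text does not support this. It does not fill the gap, because the dose branch has no figure of its own.

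Second, the loss depends on shapes that the documents do not specify. This also stands: with a step between 8 and 24 IU, or an effect at 48 IU only, the three-dose test keeps 87% or 95%. A flat statement that dose comparisons have far less power is therefore not supported. Nor should a full plateau be shown as 5% power: that is the type I error rate where no target engagement exists. And 48 versus 24 IU is a weak pair to present alone, since the definition accepts any dose difference.

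Third, at equal d and rho a dose pair and a dose-placebo pair have equal power, and some of the fall comes from moving from an omnibus to a pairwise test. True, but under the first three shapes 48 IU versus placebo keeps 97% with the same pairwise test, so the smaller gap between doses also matters.

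Fourth, d=0.32 might be read as the sizing effect. It is not: it is an expectation for behavioral measures, the sizing figure is d=0.2, and imaging effects are expected to be larger. The calculation above does not use 0.32.

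Finally, the plan nowhere says that a null dose result will be read as evidence against target engagement. That remains a risk of interpretation.

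**Conclusion.** The concern holds in a conditional form. The 95% at N=50, and the N=25 statement, concern four conditions with placebo among them and do not carry over to target engagement as the plan defines it. Taking the 95% as given, power among the three doses at N=50 is about 43% to 83% for the four graded or saturating shapes tried, and 87% to 95% for the step and 48-IU-only shapes. A literal d=0.2 between two doses has about 28% at N=50 and 19% at N=30 (rho=0.5), with 22% to 87% at N=50 for rho from 0.3 to 0.9. These figures rest on alpha 0.05, sphericity and the assumed shapes and correlations.

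Separately, and whatever the shape, the four-condition ANOVA does not isolate target engagement, because placebo alone can make it significant. The documents do not show that the dose comparison is underpowered under every plausible response; they show that its power was never stated.

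**What to change.** In the power paragraph of Statistical analysis, restrict the 95% to the four-condition test and state the alpha, within-subject correlation and effect metric (d or f) behind it. Add the power, or the detectable difference, of a placebo-free contrast among 8, 24 and 48 IU at N=50, 30 and 25 under stated dose-response shapes.

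In the aim 1 analysis, rest the target-engagement conclusion on that placebo-free contrast, reported with its confidence interval, and keep the comparisons with placebo for the oxytocin effect.

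The cost is a short recalculation and revised wording, with no extra patients. The downside is a less favourable stated power for target engagement.
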